# **Secondary Objectives:**

- To compare children's negative behavioral responses (behavioral distress, perception of pain, sensory discomfort - secondary outcomes) during dental cleanings in the SADE vs. RDE.
- b) To test the degree to which physiological anxiety mediates the SADE intervention's effects on children's negative behavioral responses.
- c) To test the degree to which specific child characteristics moderate the SADE intervention's effects on children's physiological and negative behavioral responses during dental cleaning.
- d) To compare the SADE intervention to the RDE on quality of care, cost-effectiveness, and potential cost savings of dental cleaning.

# 3.2 Study Outcome Measures

# 3.2.1 Outcome Measures for the Primary Objective

Our primary outcome measure is children's physiological response measured by EDA during the dental cleaning. EDA will be measured using the BIOPAC Systems, Inc. MP150 System. This physiological response is caused by sympathetic nervous system activation, which increases during stressful or painful situations. Sensors will be placed on the child's fingers and EDA recordings will be made immediately prior to and continuously throughout each cleaning. Two measures of tonic EDA will be collected: skin conductance level (SCL) and frequency of non-specific skin conductance responses (NS-SCR). See Table 1.

Table 1. Primary outcome measure of children's physiological responses for the SADE-2 Study.

Outcome measure (Completed by)	Measure & Description	Type of Measure (No. of Items)	When Administered	Specific Objective Tested	CRF Name (#)
Physiological Anxiety (Researcher- coded)	Electrodermal Activity (skin conductance level and frequency of non- specific responses) assesses level of sympathetic nervous system activation.	Psycho- physiological (N/A: scoring is continuous throughout recording)	Recorded at baseline and throughout both dental cleanings.	1	Scored EDA Form (23)

# 3.2.2 Outcome Measures for the Secondary Objectives

Our secondary outcome measures will consist of five behavioral indicators of distress (observational coding of behavioral distress from video-recordings, dentist-reported measures of child anxiety and cooperation, child self-report of pain, and child self-report of discomfort with sensory stimuli), measures of mediating factors, measures of moderating factors, and measures of cost-savings and quality of care.

# Secondary Objective (a): Negative Behavioral Responses

**Distress Behavior** will be measured by video-coding of child's behavior during the cleaning and coded by the researcher using the Children's Dental Behavior Rating Scale, and dentist-report (Frankl Scale and Anxiety and Cooperation Scale). The Children's Dental Behavior Rating Scale (CDBRS) was developed and pilot-tested prior to the initiation of our previous R34 pilot study, and was found to have inter-rater reliability on children both with and without ASD, *K*=.97, p<.001.  The Frankl Scale  is one of the most commonly used rating scales to assess children's behavior in the dental office  and is universally utilized by both researchers and clinicians.  The scale has high inter-rater reliability and acceptable validity,  and has been shown to significantly correlate with other behavioral indices that are used to assess anxiety and behavior during dental treatment.  The Anxiety and Cooperation Scale  assesses children's anxiety, fear, and cooperation as rated by dentists and has established reliability and validity. 

**Perception of Pain** will be measured by child self-report utilizing the Faces Pain Scale-Revised (FPS-R), which has established validity and is supported by a high positive correlation with a visual analogue scale in children aged 5 to 12 years.

**Discomfort with sensory stimuli** will be measured by child self-report utilizing the Dental Sensory Sensitivity Scale. This tool was developed and pilot-tested alongside the CDBRS, and in our pilot study was sensitive to differences between the SADE and RDE in the ASD group (effect size = .69, p<.05).

# **Secondary Objective (b): Mediating Factors**

Outcome measures include physiological anxiety (EDA) as a mediator of negative behavior (for EDA details see above Section 3.2.1).

# **Secondary Objective (c): Moderating Factors**

To test the effect of child characteristics as moderators of SADE, outcome measures will include age, autism severity, cognitive ability, sensory sensitivity, and anxiety.

# Secondary Objective (d): Cost-Savings and Quality of Care

Outcome measures include relative cost of services provided (time to complete cleaning, number of staff required, anesthesia required), ascertained by videotaped encounters. Efficacy of dental cleaning will be assessed via coded observations of plaque index before and after dental cleanings, coded from images captured via intraoral camera.

Table 2. Secondary outcome measures of the SADE-2 Study.

Outcome measure (Completed by)	Measure & Description	Type of Measure (No. of Items)	When Administered	Specific Objective Tested	CRF Name (#)
Distress Behavior (Researcher- coded from video-recording)	Children's Dental Behavior Rating Scale, a psychometrically sound tool developed for our R34 pilot study that assesses overt distress behavior.	Observational: Coding of video- recordings (5 items, each scored the first 5 minutes of prophylaxis)	Video- recordings occur during both dental cleanings; coding occurs at a later time.	2a	Children's Dental Behavior Rating Scale (22)
Distress Behavior (Anxiety and Cooperation) (Dentist-report)	Anxiety and Cooperation Scale, 65 a reliable and valid tool for use during dental cleaning to assess anxiety and cooperation. 66	Questionnaire (1)	Immediately following both dental cleanings.	2a	Behavioral Indices Form (14)
Distress Behavior (Uncooperative Behavior) (Dentist-report)	Frankl Scale, 67 a reliable and valid tool for use during dental cleaning to assess behavior.	Questionnaire (1)	Immediately following both dental cleanings.	2a	Behavioral Indices Form (14)
Perception of Pain (Child-Report)	Faces Pain Scale- Revised,  a valid tool comprised of six faces to assess perception and intensity of pain.	Questionnaire (1)	Immediately following both dental cleanings.	2a	Faces Pain Scale-Revised (17)

Discomfort with Sensory Stimuli (Child-Report)	Dental Sensory Sensitivity Scale describes the presence and magnitude of discomfort with different sensory stimuli in the dental environment.	Questionnaire (6)	Immediately following both dental cleanings.	2a	Dental Sensory Sensitivity Scale (18)
Cost-Savings (Researcher- scored)	Duration of dental cleaning, calculated from video-recordings and notes.	Observational (1)	Immediately following both dental cleanings.	2d	Cost- Effectiveness & Cost-Savings Form (21)
Cost-Savings (Researcher- scored)	Number of hands required for restraint, calculated from video-recordings and notes.	Observational (1)	Immediately following both dental cleanings.	2d	Cost- Effectiveness & Cost-Savings Form (21)
Cost-Savings (Researcher- scored, in consultation with dentist)	Need for protective stabilization, sedation, and/or anesthesia to complete cleaning.	Observational (1)	Immediately following both dental cleanings.	2d	Cost- Effectiveness & Cost-Savings Form (21)
Quality of Care (Dentist-scored)	Analysis of oral health and plaque before cleaning versus after cleaning using intra-oral photographs 90 (Rechmann et al., 2014) utilizing the Oral Health Index-Simplified  and Plaque Index. 	Observational, completion of OHI-S (12) and Plaque Index (6) based on intra-oral photographs.	Intra-oral photographs taken before and after dental cleaning; scoring to be completed at a later time.	2d	Quality of Care Recording Form (16)

Table 3. Child-descriptor variables

Child- descriptor (Completed by)	Child-descriptor & Description	Type of form (No. of Items)	When Administered	Specific Objective Tested	CRF Name (#)
ASD Diagnosis (Psychologist)	The Autism Diagnostic Observation Schedule-2 (ADOS-2) is used to confirm a diagnosis of ASD and provides a measure of autism severity.	Observational (varies)	Visit 2	2c	Autism Diagnostic Observation Schedule-2
IQ (Psychologist)	Wechsler Abbreviated Scale of Intelligence – Second Edition provides a measure of IQ	Observational (varies)	Visit 2	2c	Wechsler Abbreviated Scale of Intelligence – Second Edition
Short Sensory Profile-2 (Parent)	Sensory Sensitivity	Parent questionnaire (34)	Visit 1	2c	Sensory: Short Sensory Profile-2 (7)
Dental Anxiety (parent)	Children's Fear Survey Schedule- Dental Subscale measures dental anxiety.	Parent questionnaire (15)	Visit 1	2c	Children's Fear Survey Schedule- Dental Subscale (8)
General Anxiety (parent)	Child and Adolescent Symptom Inventory-4, Anxiety Scale	Parent questionnaire (21)	Visit 1	2c	Child and Adolescent Symptom Inventory-4, Anxiety Scale (6)
Expressive Communication Ability	Vineland Adaptive Behavior Scales-II, Expressive Communication Domain	Parent questionnaire (varies)	Visit 1	2c	Vineland Adaptive Behavior Scales- II, Expressive Communication Domain
Age of child (parent)	Age	Parent questionnaire (1)	Visit 1	2c	Family information (5)

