- c) We will enact a sequential procedure, for each research participant undergoing the SADE that consists of: (1) prior to the treatment, explaining each component of the intervention (both through a social story and verbally) and getting the child's assent (when able); (2) requiring the research team to monitor any negative reactions to the SADE adaptations; and (3) having the dental assistant or dentist remove or minimize offending stimuli that emerge during the above steps (or terminate cleaning if necessary).
- d) The study will have a data safety monitoring committee (CSOC) which will review all adverse events in an effort to ensure the welfare of all research participants.
- e) During the time of the COVID-19 pandemic, participants are at a small risk of contracting the virus when they leave their home and come to CHLA. CHLA has launched extensive protective measures to prevent the spread of the novel coronavirus and keep patients, families and team members safe.

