# 12.4 Final Analysis Plan

Descriptive statistics will be performed for all variables of interest to describe the participant population at baseline, including attrition rate and missing data, to compare those randomized to SADE first vs. those randomized to RDE first. We anticipate a low attrition rate (~10%) and will impute missing data for intent-to-treat analyses using Markov Chain Monte Carlo (MCMC)

imputation with multiple values imputer for each missing value averaged for an estimation for analyses. Bivariate associations between outcomes (physiological anxiety and children's negative behavioral responses), environment (SADE or RDE), and covariates (age, gender, order of visit, autism severity, IQ, and sensory sensitivity) will be described. The primary objective of determining difference between dental environments will be tested using intent-to-treat models examining the within-subject factor of dental environment (SADE vs RDE) using repeated measures ANCOVA for each outcome. *A priori* covariates include age (continuous), randomized order of visit, gender, and temperature. Other participant characteristics that are unbalanced between order of visits will be included as covariates *ad hoc*.

The secondary objective of examining the mediating effect of physiologic response on behavioral outcomes will be tested by first examining the bivariate relationships between EDA and behavioral outcomes, and then adding EDA estimates (SCL and NS-SCR) to models of dental environment difference on behavioral outcomes, and examining the change in the within group coefficients. A change in coefficient >15% will be considered evidence of mediation. While we have several outcomes, we specify only one mediator, thus we will apply a rational approach to examination of multiple outcomes, and will assess the fidelity of our study by estimating effect sizes (Cohen's d) of the dental environment before and after the mediation factors are assessed to confirm that statistical results were supported by clinical relevance of findings. If physiological anxiety does mediate the environment's effect on negative behavioral responses, we anticipate that the anticipated effect of environment will be eliminated once we add in EDA to the models specified in Hypothesis 2. Analyses will be performed using SPSS (v.22); a priori two-sided  $\square = 0.05$ .

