## Secondary Objective 5: Hypotheses 5a & 5b

Hypotheses 5a and 5b are similar, examining the environment difference on the costs and quality of care. The general model is presented below. Quality of care will be determined by scoring of pre- vs. post- intra-oral photographs on the OHI-S and Plaque Index measures. Health care costs are defined as personnel time burden, including direct costs of the intervention (e.g., training, materials, overhead, and direct patient care). The cost-effectiveness of the SADE intervention will be represented in the form of an incremental cost-effectiveness ratio of the cost (C) relative to the quality of care (E):  $(C_{SADE} - C_{RDE})/(E_{SADE} - E_{RDE})$ .

Hyp 5: Cost or Quality = 
$$B_0 + B_1*Environment$$

These models are paired and will involve paired t-tests or non-parametric corollary for continuous outcomes if the outcome is normal or non-normally distributed, respectively. For dichotomous outcomes (e.g., need for sedation), McNemar's test will be used to examined differences in need for the paired observations.

Cost Effectiveness Analysis. In assessment of medical interventions, cost-effectiveness evaluations become increasingly relevant. Using this evaluation approach and the comparative intervention RDE as the reference standard, the cost-effectiveness of the SADE intervention will be represented in the form of an incremental cost-effectiveness ratio as:  $(C_1 - C_0)/(E_1 - E_0)$ , where the subscript 1 refers to the SADE intervention arm and the subscript 0 refers to the RDE comparative arm.  $C_1$  represents the average net cost of implementing the intervention;  $C_0$  represents the average net cost of the RDE comparative arm;  $E_1$  represents the quality of care associated with the SADE intervention; and  $E_0$  represents the quality of care associated with RDE. We will consider alternative effectiveness outcomes.

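### A cleaning stopped for distress counts as a short, cheap visit, and any CDBRS score lost that way falls under the general imputation rule

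*Combined protocol and SAP*

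**What the plan says.** - **Early stops are foreseen.** Section 2.2.1 sets out steps for each participant undergoing the SADE, the last being "having the dental assistant or dentist remove or minimize offending stimuli that emerge during the above steps (or terminate cleaning if necessary". No matching step is written for RDE visits.
- **CDBRS window.** Table 2 (section 3.2.2) gives the coding as "5 items, each scored the first 5 minutes of prophylaxis". The text on Secondary Objective (a) is looser: "video-coding of child's behavior during the cleaning". Section 6.3 places prophylaxis after electrodes, rest period, research oral hygiene assessments, oral examination and the first photographs.
- **Missing data.** Section 12.4 says the study "will impute missing data for intent-to-treat analyses using Markov Chain Monte Carlo (MCMC"), averaging the imputed values. It makes no exception for data lost because of the child's distress.
- **Duration.** Table 2 lists "Duration of dental cleaning, calculated from video-recordings and notes" as a cost-savings outcome. The text above that table words it as "relative cost of services provided (time to complete cleaning, number of staff required, anesthesia required"). Under Hypotheses 5a and 5b, "Health care costs are defined as personnel time burden", and continuous outcomes get a paired t-test or its non-parametric counterpart.
- **Not stated.** The text provided does not say how a terminated cleaning is scored on the CDBRS or how its duration is treated.

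**The concern.** Both outcomes are affected by the event they should help to measure.

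A stopped cleaning has an observed duration, so it is not missing. It enters the paired comparison as a low value of a measure on which low means saving. Nothing separates a short, successful cleaning from a short, abandoned one. The second wording, time to complete, has no meaning for a cleaning that was not completed.

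For the CDBRS, a score lost because the child was too distressed to continue is missing for a reason tied to its own value. Standard MCMC imputation treats the loss as explained by the observed data. It therefore predicts these visits from children who tolerated prophylaxis and understates their distress.

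At stake are Hypothesis 2 (distress behaviour) and Hypothesis 5a (cost). The pilot distress effects were small, d = 0.11 to 0.23 (section 12.2), so there is little margin. If stops are more common in SADE, both errors favour SADE. If they are more common in RDE, both work against it.

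**Working it through.** **The plan's own figure.** Section 12.2 gives a detectable d of 0.22 with 165 pairs. For a paired test at two-sided 0.05 and 80% power, n = ((1.960 + 0.842)/0.22)² = 162 by the normal approximation and 165 by the t distribution. The figure reproduces at that alpha. The point does not depend on it; it only sets a plausible effect for the second illustration below.

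**Inputs from the documents.** Cleaning length 15 to 45 minutes (section 6.1); pilot distress effects up to 0.23 (section 12.2). **Assumed, because the documents are silent:** stop shares, length of a stopped visit, within-child correlation.

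**Duration.** With no true difference in the length of completed cleanings,

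shift (SADE − RDE) = (share stopped in SADE − share stopped in RDE) × (stopped length − full length).

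| RDE stopped | SADE stopped | Full / stopped length (min) | Shift, SADE − RDE (min) |
|---|---|---|---|
| 10% | 5% | 30 / 10 | (−0.05) × (−20) = +1.0 |
| 5% | 10% | 30 / 10 | (+0.05) × (−20) = −1.0 |
| 10% | 10% | 30 / 10 | 0 |

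With full lengths of 15 to 45 minutes, stopped lengths of 5 to 10 minutes and share gaps of 5 to 10 points, the size runs from 0.05 × (15 − 10) = 0.25 to 0.10 × (45 − 5) = 4.0 minutes. The environment with more stops always looks quicker.

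**CDBRS, stop shares set separately.** Simulation of 198 children (220 × 0.9), 3,000 runs, SD of the within-child difference 1, correlation 0.5, true effect −0.22 (SADE minus RDE). The most distressed visits in each environment lose their score and are predicted from the other visit.

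| RDE lost | SADE lost | Estimate after imputation |
|---|---|---|
| 5% | 5% | −0.22 |
| 10% | 5% | −0.15 |
| 15% | 5% | −0.08 |
| 20% | 10% | −0.09 |
| 5% | 10% | −0.29 |

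**CDBRS, one distress threshold for both environments.** Simulation of 165 pairs, true effect 0.23 visit-level SD in favour of SADE, correlation 0.4 to 0.8, 3,000 runs per cell. RDE has more stops here only because SADE is assumed to work.

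| RDE / SADE lost | Predicted from the other visit | Worst score set at the stopping threshold |
|---|---|---|
| 5% / 3% | 0.20–0.21 | 0.22 |
| 10% / 6.5% | 0.18–0.20 | 0.21 |
| 20% / 14% | 0.15–0.18 | 0.19 |

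If the imputation also uses a same-visit dentist rating (assumed correlation 0.6 to 0.8 with the CDBRS), the middle column becomes 0.21–0.22 at 5% and 0.19–0.21 at 10%.

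The worst-score column depends on where the worst score lies. Each SD by which it exceeds the threshold adds the gap in stop shares. At 10% / 6.5% that is 0.035, so 0.21 becomes 0.245, above the true 0.23.

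**The case against.** The case against is substantial, and most of it limits the point.

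- **Imputation of stopped visits is not stated.** A reader might infer that the plan imputes every such visit. It says only that missing data are imputed, and no section says a shortened window is missing. Both cleanings are video-recorded in full (section 8.1), so a child stopped at minute 3 of prophylaxis has footage that could be coded. The CDBRS form and manual of procedures are not in the text. This stands for partial windows. It does not help a child stopped before prophylaxis.
- **Not every stop matters.** A stop after the fifth minute of prophylaxis leaves a full CDBRS score. The simulations treat every stopped visit as lost, so they bound the effect from above for a given stop share.
- **Other outcomes record the bad visit.** The dentist's Frankl and Anxiety and Cooperation ratings (section 8.1), the restraint and stabilization or sedation items (Table 2) and the plaque scores in the cost-effectiveness denominator (section 12.4) can all register it. True, but they do not repair duration or CDBRS, which are listed separately. Post-cleaning photographs follow prophylaxis, so they may be missing too.
- **Cost is wider than duration.** Section 12.4 includes training, materials and overhead. That dilutes the error in total cost but leaves the duration comparison as it is.
- **A worst-score rule has its own bias.** It overwrites observed behaviour, and the trigger is a decision by staff who know the environment (section 5.4.2). This stands, and is why the rule belongs in a sensitivity analysis.

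**Conclusion.** The point holds in a limited form. Followed as written, the plan credits an abandoned cleaning as a time saving. It also treats a CDBRS score lost through distress like any other missing value. This touches two secondary outcomes; the primary EDA outcome is not at issue here.

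Three stronger readings are tempting but not supported:

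- **That the worst visits are scored in the wrong direction.** This fits duration only. Imputation pulls the individual CDBRS values toward typical ones.
- **That the trial is biased against SADE because RDE will have more stops.** The only termination step is written for SADE visits, and no stop rate is given for either environment.
- **That a stopped visit leaves no unfavourable trace.** Several other outcomes can record it.

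The size depends on the difference in stop shares; with equal shares both illustrations give no net shift. Under the assumed shares, duration moves by 0.25 to 4.0 minutes. A true CDBRS effect of 0.22 becomes anything from 0.08 to 0.29 with gaps of 5 to 10 points. Under the single-threshold model the loss is modest at 5% to 10% RDE stops and reaches about a third only at 20% (0.15 against 0.23).

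**What to change.** In section 12.4 and Table 2:

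1. **Derive a status variable** for each visit, cleaning completed or stopped for distress, from the full-visit video and notes. Do not rely on the Visit Completion Form, which section 6.4 describes as covering time measurements and video completion, not stops. Report the variable by environment with McNemar's test, already in the plan.
2. **Duration.** Do not count a stopped cleaning's short time as a saving. Rank it as unfavourable in the duration comparison, using the non-parametric paired test already allowed. Show actual personnel time separately for the cost calculation.
3. **CDBRS.** Code whatever prophylaxis minutes were observed. Include the same-visit Frankl and Anxiety and Cooperation ratings in the imputation model. Add a sensitivity analysis that gives the worst score to visits stopped for distress before the five-minute window is complete.

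The cost is some analysis-plan wording and one derived variable from recordings already made. Nothing changes in when or why a cleaning is stopped. The drawback is that worst rank and worst score are conventions triggered by an unblinded decision, so results should be shown with and without them.

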# 4 STUDY DESIGN

This is a Phase II clinical trial utilizes a randomized cross-over design with two conditions at a single-site to test the efficacy of the SADE intervention protocol in reducing children's physiological anxiety and negative responses.

The Phase II experimental design is overviewed in the Schematic of Study Design section of the Clinical Trial Protocol Summary (pg. 11).

